### 11.1.3 Methods for Evaluation of Measurable Disease

All measurements should be taken and recorded in metric notation using a ruler or calipers. All baseline evaluations should be performed as closely as possible to the beginning of treatment and never more than 4 weeks before the beginning of the treatment.

The same method of assessment and the same technique should be used to characterize each identified and reported lesion at baseline and during follow-up. Imaging-based evaluation is preferred to evaluation by clinical examination unless the lesion(s) being followed cannot be imaged but are assessable by clinical exam.

Clinical lesions Clinical lesions will only be considered measurable when they are superficial (*e.g.*, skin nodules and palpable lymph nodes) and  $\geq 10$  mm diameter as assessed using calipers (*e.g.*, skin nodules). In the case of skin lesions, documentation by color photography, including a ruler to estimate the size of the lesion, is recommended.

Chest x-ray Lesions on chest x-ray are acceptable as measurable lesions when they are clearly defined and surrounded by aerated lung. However, CT is preferable.

Conventional CT and MRI This guideline has defined measurability of lesions on CT scan based on the assumption that CT slice thickness is 5 mm or less. If CT scans have slice thickness greater than 5 mm, the minimum size for a measurable lesion should be twice the slice thickness. MRI is also acceptable in certain situations (*e.g.* for body scans).

Use of MRI remains a complex issue. MRI has excellent contrast, spatial, and temporal resolution; however, there are many image acquisition variables involved in MRI, which greatly impact image quality, lesion conspicuity, and measurement. Furthermore, the availability of MRI is variable globally. As with CT, if an MRI is performed, the technical specifications of the scanning sequences used should be optimized for the evaluation of the type and site of disease. Furthermore, as with CT, the modality used at follow-up should be the same as was used at baseline and the lesions should be measured/assessed on the same pulse sequence. It is beyond the scope of the RECIST guidelines to prescribe specific MRI pulse sequence parameters for all scanners, body parts, and diseases. Ideally, the same type of scanner should be used and the image acquisition protocol should be followed as closely as possible to prior scans. Body scans should be performed with breath-hold scanning techniques, if possible.

PET-CT At present, the low dose or attenuation correction CT portion of a combined PET-CT is not always of optimal diagnostic CT quality for use with RECIST measurements. However, if the site can document that the CT performed as part of a PET-CT is of identical diagnostic quality to a diagnostic CT (with IV and oral contrast), then the CT portion of the PET-CT can be used for RECIST measurements and can be used interchangeably with conventional CT in accurately measuring cancer lesions over time. Note, however, that the PET portion of the CT introduces additional data which

may bias an investigator if it is not routinely or serially performed.

Ultrasound Ultrasound is not useful in assessment of lesion size and should not be used as a method of measurement. Ultrasound examinations cannot be reproduced in their entirety for independent review at a later date and, because they are operator dependent, it cannot be guaranteed that the same technique and measurements will be taken from one assessment to the next. If new lesions are identified by ultrasound in the course of the study, confirmation by CT or MRI is advised. If there is concern about radiation exposure at CT, MRI may be used instead of CT in selected instances.

Endoscopy, Laparoscopy The utilization of these techniques for objective tumor evaluation is not advised. However, such techniques may be useful to confirm complete pathological response when biopsies are obtained or to determine relapse in trials where recurrence following complete response (CR) or surgical resection is an endpoint.

Tumor markers Tumor markers alone cannot be used to assess response. If markers are initially above the upper normal limit, they must normalize for a patient to be considered in complete clinical response. Specific guidelines for both CA-125 response (in recurrent ovarian cancer) and PSA response (in recurrent prostate cancer) have been published [JNCI 96:487-488, 2004; J Clin Oncol 17, 3461-3467, 1999; J Clin Oncol 26:1148-1159, 2008]. In addition, the Gynecologic Cancer Intergroup has developed CA-125 progression criteria which are to be integrated with objective tumor assessment for use in first-line trials in ovarian cancer [JNCI 92:1534-1535, 2000].

Cytology, Histology These techniques can be used to differentiate between partial responses (PR) and complete responses (CR) in rare cases (*e.g.*, residual lesions in tumor types, such as germ cell tumors, where known residual benign tumors can remain).

The cytological confirmation of the neoplastic origin of any effusion that appears or worsens during treatment when the measurable tumor has met criteria for response or stable disease is mandatory to differentiate between response or stable disease (an effusion may be a side effect of the treatment) and progressive disease.

FDG-PET While FDG-PET response assessments need additional study, it is sometimes reasonable to incorporate the use of FDG-PET scanning to complement CT scanning in assessment of progression (particularly possible 'new' disease). New lesions on the basis of FDG-PET imaging can be identified according to the following algorithm:

- a. Negative FDG-PET at baseline, with a positive FDG-PET at follow-up is a sign of PD based on a new lesion.
- b. No FDG-PET at baseline and a positive FDG-PET at follow-up: If the positive FDG-PET at follow-up corresponds to a new site of disease confirmed by CT, this is PD. If the positive FDG-PET at follow-up is not confirmed as a new site of disease on CT, additional follow-up CT scans are needed to determine if there is truly progression occurring at that site (if so, the date of PD will be the date of the initial abnormal FDG-PET scan). If the positive FDG-PET at follow-up corresponds to a pre-existing site of disease on CT that is not progressing on the basis of the anatomic images, this

is not PD.

- c. FDG-PET may be used to upgrade a response to a CR in a manner similar to a biopsy in cases where a residual radiographic abnormality is thought to represent fibrosis or scarring. The use of FDG-PET in this circumstance should be prospectively described in the protocol and supported by disease-specific medical literature for the indication. However, it must be acknowledged that both approaches may lead to false positive CR due to limitations of FDG-PET and biopsy resolution/sensitivity.

Note: A 'positive' FDG-PET scan lesion means one which is FDG avid with an uptake greater than twice that of the surrounding tissue on the attenuation corrected image.

#### 11.1.4 Response Criteria

##### 11.1.4.1. Evaluation of Target Lesions

Complete Response (CR): Disappearance of all target lesions. Any pathological lymph nodes (whether target or non-target) must have reduction in short axis to <10 mm.

Partial Response (PR): At least a 30% decrease in the sum of the diameters of target lesions, taking as reference the baseline sum diameters.

Progressive Disease (PD): At least a 20% increase in the sum of the diameters of target lesions, taking as reference the smallest sum on study (this includes the baseline sum if that is the smallest on study). In addition to the relative increase of 20%, the sum must also demonstrate an absolute increase of at least 5 mm. (Note: the appearance of one or more new lesions is also considered progressions).

Stable Disease (SD): Neither sufficient shrinkage to qualify for PR nor sufficient increase to qualify for PD, taking as reference the smallest sum diameters while on study.

##### 11.1.4.2. Evaluation of Non-Target Lesions

Complete Response (CR): Disappearance of all non-target lesions and normalization of tumor marker level. All lymph nodes must be non-pathological in size (<10 mm short axis).

Note: If tumor markers are initially above the upper normal limit, they must normalize for a patient to be considered in complete clinical response.

Non-CR/Non-PD: Persistence of one or more non-target lesion(s) and/or maintenance of tumor marker level above the normal limits.

Progressive Disease (PD): Appearance of one or more new lesions and/or *unequivocal progression* of existing non-target lesions. *Unequivocal progression* should not normally trump target lesion status. It must be representative of overall

disease status change, not a single lesion increase.

Although a clear progression of “non-target” lesions only is exceptional, the opinion of the treating physician should prevail in such circumstances, and the progression status should be confirmed at a later time by the review panel (or Principal Investigator).

#### 11.1.4.3. Evaluation of Best Overall Response

The best overall response is the best response recorded from the start of the treatment until disease progression/recurrence (taking as reference for progressive disease the smallest measurements recorded since the treatment started). The patient's best response assignment will depend on the achievement of both measurement and confirmation criteria.

#### For Patients with Measurable Disease (*i.e.*, Target Disease)

Target Lesions	Non-Target Lesions	New Lesions	Overall Response	Best Overall Response when Confirmation is Required*
CR	CR	No	CR	≥4 wks. Confirmation**
CR	Non-CR/Non-PD	No	PR	≥4 wks. Confirmation**
CR	Not evaluated	No	PR	
PR	Non-CR/Non-PD/not evaluated	No	PR	
SD	Non-CR/Non-PD/not evaluated	No	SD	Documented at least once ≥4 wks. from baseline**
PD	Any	Yes or No	PD	no prior SD, PR or CR
Any	PD***	Yes or No	PD	
Any	Any	Yes	PD	

* See RECIST 1.1 manuscript for further details on what is evidence of a new lesion.  ** Only for non-randomized trials with response as primary endpoint.  *** In exceptional circumstances, unequivocal progression in non-target lesions may be accepted as disease progression.
 
Note: Patients with a global deterioration of health status requiring discontinuation of treatment without objective evidence of disease progression at that time should be reported as “symptomatic deterioration.” Every effort should be made to document the objective progression even after discontinuation of treatment.
				

#### For Patients with Non-Measurable Disease (*i.e.*, Non-Target Disease)

Non-Target Lesions	New Lesions	Overall Response
CR	No	CR
Non-CR/non-PD	No	Non-CR/non-PD*
Not all evaluated	No	not evaluated
Unequivocal PD	Yes or No	PD
Any	Yes	PD
* 'Non-CR/non-PD' is preferred over 'stable disease' for non-target disease since SD is increasingly used as an endpoint for assessment of efficacy in some trials so to assign this category when no lesions can be measured is not advised		

#### 11.1.5 Duration of Response

Duration of overall response: The duration of overall response is measured from the time measurement criteria are met for CR or PR (whichever is first recorded) until the first date that recurrent or progressive disease is objectively documented (taking as reference for progressive disease the smallest measurements recorded since the treatment started).

The duration of overall CR is measured from the time measurement criteria are first met for CR until the first date that progressive disease is objectively documented.

Duration of stable disease: Stable disease is measured from the start of the treatment until the criteria for progression are met, taking as reference the smallest measurements recorded since the treatment started, including the baseline measurements.

#### 11.1.6 Progression-Free Survival

PFS is defined as the duration of time from start of treatment to time of progression or death, whichever occurs first.

#### 11.1.7 Response Review

All responses will be reviewed by an expert(s) independent of the study at the study's completion. Simultaneous review of the patients' files and radiological images will occur.

### 11.2. Other Response Parameters

N/A

## 12. DATA REPORTING / REGULATORY REQUIREMENTS

Adverse event lists, guidelines, and instructions for AE reporting can be found in [Section 7.0](#) (Adverse Events: List and Reporting Requirements).

## 12.1. Data Reporting

### 12.1.1 Method

This study will be monitored by the Clinical Data Update System (CDUS) Version 3.0. Cumulative protocol- and patient-specific CDUS data will be submitted electronically to CTEP on a quarterly basis, either by FTP burst of data or via the CDS web application. Reports are due January 31, April 30, July 31, and October 31. Instructions for submitting data using the CDUS can be found on the CTEP Web site (<http://ctep.cancer.gov/reporting/cdus.html>).

**Note:** If your study has been assigned to CDUS-Complete reporting, **all** adverse events (both routine and expedited) that have occurred on the study and meet the mandatory CDUS reporting guidelines must be reported via the monitoring method identified above. If your study has been assigned to CDUS-Abbreviated reporting, no adverse event reporting (routine or expedited) is required to be reported via CDUS.

### 12.1.2 Responsibility for Data Submission

Study participants are responsible for submitting CDUS data and/or data forms to either the Coordinating Center or to the Lead Organization on the study quarterly. The date for submission to the Coordinating Center or to the Lead Organization will be set by them. CDUS does not accept data submissions from the participants on the study. When setting the dates, allow time for Coordinating Center compilation, Principal Investigator review, and timely submission to CTEP by the quarterly deadlines (see **Section 12.1.1**). For trials monitored by CTMS, a quarterly report of data will be provided by Theradex to the Coordinating Center.

Either the Coordinating Center or the Lead Organization is responsible for compiling and submitting CDUS data to CTEP for all participants and for providing the data to the Principal Investigator for review.

## 12.2. CTEP Multicenter Guidelines

This protocol will adhere to the policies and requirements of the CTEP Multicenter Guidelines. The specific responsibilities of the Principal Investigator and the Coordinating Center (Study Coordinator) and the procedures for auditing are presented in [Appendix B](#).

- The Principal Investigator/Coordinating Center is responsible for distributing all IND Action Letters or Safety Reports received from CTEP to all participating institutions for submission to their individual IRBs for action as required.
- Except in very unusual circumstances, each participating institution will order DCTD-supplied agents directly from CTEP. Agents may be ordered by a participating site only after the initial IRB approval for the site has been forwarded by the Coordinating Center to the CTEP PIO ([contact]) except for Group studies.

### 12.3. Collaborative Agreements Language

The agent(s) supplied by CTEP, DCTD, NCI used in this protocol is/are provided to the NCI under a Collaborative Agreement (CRADA, CTA, CSA) between the Pharmaceutical Company(ies) (hereinafter referred to as “Collaborator(s)”) and the NCI Division of Cancer Treatment and Diagnosis. Therefore, the following obligations/guidelines, in addition to the provisions in the “Intellectual Property Option to Collaborator” ([http://ctep.cancer.gov/industryCollaborations2/intellectual\\_property.htm](http://ctep.cancer.gov/industryCollaborations2/intellectual_property.htm)) contained within the terms of award, apply to the use of the Agent(s) in this study:

1. Agent(s) may not be used for any purpose outside the scope of this protocol, nor can Agent(s) be transferred or licensed to any party not participating in the clinical study. Collaborator(s) data for Agent(s) are confidential and proprietary to Collaborator(s) and shall be maintained as such by the investigators. The protocol documents for studies utilizing Agents contain confidential information and should not be shared or distributed without the permission of the NCI. If a copy of this protocol is requested by a patient or patient’s family member participating on the study, the individual should sign a confidentiality agreement. A suitable model agreement can be downloaded from: <http://ctep.cancer.gov>.
2. For a clinical protocol where there is an investigational Agent used in combination with (an)other Agent(s), each the subject of different Collaborative Agreements, the access to and use of data by each Collaborator shall be as follows (data pertaining to such combination use shall hereinafter be referred to as "Multi-Party Data"):
  - a. NCI will provide all Collaborators with prior written notice regarding the existence and nature of any agreements governing their collaboration with NCI, the design of the proposed combination protocol, and the existence of any obligations that would tend to restrict NCI's participation in the proposed combination protocol.
  - b. Each Collaborator shall agree to permit use of the Multi-Party Data from the clinical trial by any other Collaborator solely to the extent necessary to allow said other Collaborator to develop, obtain regulatory approval or commercialize its own Agent.
  - c. Any Collaborator having the right to use the Multi-Party Data from these trials must agree in writing prior to the commencement of the trials that it will use the Multi-Party Data solely for development, regulatory approval, and commercialization of its own Agent.
3. Clinical Trial Data and Results and Raw Data developed under a Collaborative Agreement will be made available to Collaborator(s), the NCI, and the FDA, as appropriate and unless additional disclosure is required by law or court order as described in the IP Option to Collaborator ([http://ctep.cancer.gov/industryCollaborations2/intellectual\\_property.htm](http://ctep.cancer.gov/industryCollaborations2/intellectual_property.htm)). Additionally, all Clinical Data and Results and Raw Data will be collected, used and disclosed consistent with all applicable federal statutes and regulations for the protection of human subjects, including, if applicable, the *Standards for Privacy of Individually*

*Identifiable Health Information* set forth in 45 C.F.R. Part 164.

4. When a Collaborator wishes to initiate a data request, the request should first be sent to the NCI, who will then notify the appropriate investigators (Group Chair for Cooperative Group studies, or PI for other studies) of Collaborator's wish to contact them.
5. Any data provided to Collaborator(s) for Phase 3 studies must be in accordance with the guidelines and policies of the responsible Data Monitoring Committee (DMC), if there is a DMC for this clinical trial.
6. Any manuscripts reporting the results of this clinical trial must be provided to CTEP by the Group office for Cooperative Group studies or by the principal investigator for non-Cooperative Group studies for immediate delivery to Collaborator(s) for advisory review and comment prior to submission for publication. Collaborator(s) will have 30 days from the date of receipt for review. Collaborator shall have the right to request that publication be delayed for up to an additional 30 days in order to ensure that Collaborator's confidential and proprietary data, in addition to Collaborator(s)'s intellectual property rights, are protected. Copies of abstracts must be provided to CTEP for forwarding to Collaborator(s) for courtesy review as soon as possible and preferably at least three (3) days prior to submission, but in any case, prior to presentation at the meeting or publication in the proceedings. Press releases and other media presentations must also be forwarded to CTEP prior to release. Copies of any manuscript, abstract and/or press release/ media presentation should be sent to:

Email: [[contact]](mailto:[contact])

The Regulatory Affairs Branch will then distribute them to Collaborator(s). No publication, manuscript or other form of public disclosure shall contain any of Collaborator's confidential/proprietary information.

## **13 STATISTICAL CONSIDERATIONS**

### **13.1 Study Overview**

This is an open label, two-stage phase II study designed to assess the proportion of patients who have a partial or complete response to treatment with trametinib in advanced TNBC patients, followed by trametinib in combination with AKT inhibitor GSK2141795 at time of tumor progression (Figure 1, [Schema](#)). Preclinical data from the Ohio State University and others suggest that a subset of triple negative breast cancer (TNBC) patients that are PTEN wild type may demonstrate sensitivity to single agent MEK inhibition (Unpublished [name], [name]), and dual targeting of the RAS/RAF/MEK/ERK pathway and PI3K/AKT pathways may result in durable response after progression on MEK inhibitor monotherapy. Therefore, we have two parts to this study, where the primary driving hypotheses are two-fold: (1) that the anti-tumor response to the single agent trametinib will depend on the PTEN status of the tumor, with wild type PTEN having a higher likelihood of response than PTEN

null tumors; and (2) that simultaneous inhibition of the RAS/RAF/MEK and PI3K/AKT pathway with trametinib and GSK2141795 will overcome both intrinsic and acquired resistance to trametinib monotherapy. In addition to evaluating clinical efficacy of this regimen, we will also assess correlative markers in relation to clinical outcomes of interest. Part 1 focuses on evaluation of efficacy after treatment with single agent trametinib, and Part 2 is focused on evaluating salvage efficacy of treatment with the combination of trametinib and GSK2141795 in patients who progress on trametinib alone.

### 13.1.1 Primary Endpoint

The primary endpoint for this trial is the objective response rate, defined as the proportion of patients who have had a partial response (PR) or complete response (CR) within the first 6 months after initiation of therapy with trametinib. All eligible patients who have received at least one dose of the study regimen will be evaluable for response. Participants will be re-evaluated for response every 2 cycles (8 weeks). Response, stable disease and progression will be evaluated using the international criteria proposed by the Response Evaluation Criteria in Solid Tumors (RECIST) version 1.1 guideline. In addition to a baseline scan, confirmatory scans will be obtained after approximately 8 weeks following initial documentation of a clinical benefit.

In determining this rate, the number of patients with RECIST 1.1 based PR or CR will be divided by the number of evaluable patients. All evaluable patients will be used for this analysis. Evaluable patients will be defined as only those participants who have received at least one cycle of therapy, and have had their disease re-evaluated. Exact binomial 95% confidence intervals for the true PR+CR response rate will be calculated.

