#### **5.6. Criteria for Removal from Study**

Patients will be removed from study when any of the criteria listed in [Section 5.4](#) applies. The reason for study removal and the date the patient was removed must be documented in the Case Report Form.

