Tumor measurements 	X	Staging will occur after every 2 cycles $\pm$ 7 days or as Clinically Indicated			
Adverse Events		Continuous			
Follow Up Data 					X

1. Assessments scheduled on days of dosing should be done prior to administration of study drug(s), unless otherwise specified.
2. Tumor measurements within 4 weeks of first dose. Documentation (radiologic) must be provided for patients removed from study for progressive disease. If subject was withdrawn due to progression of disease (PD), disease assessments do not need to be repeated at the Final Study Visit. CT chest/abdomen/pelvis preferred. Bone scan, MRI, PET scan may be used at the discretion of the treating physician.
3. Final Study Visit should occur 21 days ( $\pm$ 7 days) after last dose of study drug. Follow up will continue for 52 weeks after removal from study or until death, whichever occurs first. Follow up will be every 3 months to confirm patient's living status and whether the patient has progressed (if patient did not progress on protocol therapy) gathered from clinic notes or telephone calls (no patient visit required).
4. Should include alkaline phosphatase, total bilirubin, creatinine, glucose, potassium, SGOT, SGPT, sodium.
5. Perform only in women of child-bearing potential.
6. Ophthalmic exam will include indirect and direct fundoscopy, visual acuity, visual field examination, tonometry and color fundus photos. Additional ophthalmic exams will be performed if symptomatically warranted.

Study Assessment s 	Screen	Part 1 Trametinib monotherapy	Part 2 Trametinib in combination with GSK2141795	Final Study Visit 	Post Treatment Follow Up 
---------------------------------	--------	-------------------------------------	---	-----------------------------------	--

7. Whole blood (6 mL) should be collected in an EDTA tube and stored at -70°C or below until shipping.
8. Plasma should be purified from 10 mL of blood collected in an EDTA tube. Aliquots should be stored at -70°C or below until shipping.
9. Research biopsies may include breast core biopsy, skin or chest wall biopsy, lymph node biopsy, liver biopsy, or lung biopsy.

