#### 11.1.1 Definitions

Evaluable for toxicity. All patients will be evaluable for toxicity from the time of their first treatment with trametinib and GSK 214179.

Evaluable for objective response. Only those patients who have measurable disease present at baseline, have received at least one cycle of therapy, and have had their disease re-evaluated will be considered evaluable for response. These patients will have their response classified according to the definitions stated below. (Note: Patients who exhibit objective disease progression prior to the end of cycle 1 will also be considered evaluable)

Evaluable Non-Target Disease Response. Patients who have lesions present at baseline that are evaluable but do not meet the definitions of measurable disease, have received at least one cycle of therapy, and have had their disease re-evaluated will be considered evaluable for non-target disease. The response assessment is based on the presence, absence, or unequivocal progression of the lesions.

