### 13.2. Sample Size, Accrual, and Study Duration:

This study design requires a minimum of 12 and a maximum of 37 evaluable patients. In addition, we expected to accrue an additional 10% to accommodate the potential for problem cases (i.e. patients who are not evaluable for some reason). The first 45 evaluable patients will be used in the decision analysis for this part of the trial, and estimates will also be generated using all evaluable patients. We expect approximately 3 breast cancer patients to be enrolled per month. This will translate to a total of 26 months to accrue a maximum of 50 patients and allowing for the 6 months interim analysis in both Part 1 and Part 2.

The number of patients inevaluable due to screen failure was higher than expected. As such, a total of 50 patients were consented across all sites in order to enroll 37 evaluable patients

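### Section 13.1.1 gives two incompatible denominators for the primary response rate; the narrower one conflicts with Sections 13.3 and 13.5.2 and would usually overstate the rate

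*Combined protocol and SAP*

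**What the plan says.** Section 13.1.1 defines the primary endpoint as the proportion with a partial or complete response "within the first 6 months after initiation of therapy with trametinib". On who is counted, the documents give several statements:

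- **Section 13.1.1, first paragraph:** "All eligible patients who have received at least one dose of the study regimen will be evaluable for response".
- **Section 13.1.1, second paragraph**, which gives the formula (responders divided by evaluable patients): "Evaluable patients will be defined as only those participants who have received at least one cycle of therapy, and have had their disease re-evaluated".
- **Section 11.1.1:** patients with measurable disease at baseline who "have received at least one cycle of therapy, and have had their disease re-evaluated will be considered evaluable for response", with a note that "Patients who exhibit objective disease progression prior to the end of cycle 1 will also be considered evaluable". Section 13.1.1 has no such note.
- **Section 13.3, under Part 2 but speaking of the primary outcome:** a patient who cannot tolerate trametinib or goes off study in Part 1 stays in the analyses and the decision rule.
- **Section 13.5.2:** the main response analysis includes all eligible patients, except possibly those never dosed. Response categories 4 to 9, which include early deaths and unknowns, are failures. Sub-analyses that exclude patients, for example for early discontinuation, cannot support efficacy conclusions.

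Section 13.2 sets the size: "This study design requires a minimum of 12 and a maximum of 37 evaluable patients". It also says that the first 45 evaluable patients enter the decision analysis. Section 13.3 places the Part 1 looks at 12 and 37 evaluable patients. Neither section says which meaning of evaluable applies.

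**The concern.** The two sentences in Section 13.1.1 differ for any patient who is dosed but stops before completing a cycle, or who is never re-evaluated. The first sentence keeps that patient in the denominator and the second removes the patient. A patient with no re-evaluation cannot be a recorded responder, and one who took less than a cycle rarely will be. The second sentence therefore removes treatment failures and leaves responders in place.

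The section that defines the primary endpoint attaches its formula to the kind of subset that Section 13.5.2 bars from supporting conclusions. The documents state no order of precedence among these sections, so an analyst could defend more than one denominator after seeing the data. The primary estimate and its exact 95% confidence interval would depend on that choice.

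**Working it through.** **1. The plan's own design.** Inputs from Section 13.3, Part 1: null rate 5%, target 20%, stop if there are 0 responders in 12, promising if there are at least 4 in 37. The probability of declaring promise is the sum over x = 1 to 12 of P(X₁ = x) × P(X₂ ≥ 4 − x), with X₁ ~ Bin(12, p) and X₂ ~ Bin(25, p).

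- p = 0.05: 9.3% (stated type I error 10%)
- p = 0.20: 90.2% (stated power 90%)

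The design reproduces. It requires only that the 12 and the 37 be a well-defined set.

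**2. Whom the narrower sentence removes.** The Study Calendar says "Staging will occur after every 2 cycles", that is, every 8 weeks with 28-day cycles, or when clinically indicated. A patient who leaves before week 8 might thus have no scan. However, footnote 2 of the calendar waives a repeat assessment at the Final Study Visit for patients withdrawn for progression. This implies that other withdrawals are assessed there, 21 (± 7) days after the last dose. Patients with no re-evaluation are then mainly early deaths, refusals and losses to follow-up. Patients who took less than one cycle are removed as well, even if they were re-evaluated.

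**3. What the other sections do with them.** Section 5.6 says "Patients will be removed from study when any of the criteria listed in" Section 5.4 applies. Those criteria cover progression, intercurrent illness, unacceptable adverse events, withdrawal and investigator judgment. Patients going off study in Part 1, as Section 13.3 puts it, are therefore a broad group, and that section keeps them. Section 13.5.2 counts early deaths and unknowns as failures. Both sections give the opposite answer to the second paragraph of Section 13.1.1.

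**4. Effect on the estimate.** Take 37 eligible treated patients and 4 responders, the smallest count that meets the final rule. Let k non-responders be dropped without replacement. The rate is 4/(37 − k), with Clopper-Pearson 95% limits.

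| k (assumed) | Rate | Exact 95% CI |
|---|---|---|
| 0 | 4/37 = 10.8% | 3.0 to 25.4% |
| 2 | 4/35 = 11.4% | 3.2 to 26.7% |
| 4 | 4/33 = 12.1% | 3.4 to 28.2% |

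**5. Effect on the decision.** The rule counts responders. Removing non-responders without replacing them leaves the count at 4, or at 3 if it was 3. The estimate moves and the conclusion does not.

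**The case against.** The strongest reply is that the plan already has governing text. Section 13.5.2 describes the main analysis of response, and Section 13.3 speaks directly to the Part 1 decision rule. On that view the second paragraph of Section 13.1.1 is a stray sentence. This largely holds for the decision rule. It does not settle the estimate, because the conflicting sentence stands in the section that defines the primary endpoint, is attached to the formula, and is worded as exclusive.

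A second reply is that the effect is small and may be nil, and this stands. With 2 to 4 patients dropped the rate moves by 0.6 to 1.3 percentage points, inside an interval about 22 points wide. The only excess of inevaluable patients that Section 13.2 reports is due to screen failure. Patients who fail screening are not dosed, so they fall outside both denominators.

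A third reply is that the bias need not be upward. If a patient stopped before completing a cycle and later had a response, the narrower sentence would remove a responder. With one such patient among four dropped, 4/37 becomes 3/33 = 9.1%, below the required count of 4. This is possible but should be rare. Sections 11.1.4.3 and 13.1.1 call for confirmation of response, and the Study Calendar's post-treatment follow-up records only survival and progression, without a visit. This is why the bias is described as usual and not certain.

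**Conclusion.** The contradiction is certain on the face of the text and should be corrected. The direction, usually upward, follows because the patients removed are almost always non-responders. The size in this trial is unknown: the documents give no share of treated patients who fail the narrower definition, and the shift of 0.6 to 1.3 points rests on an assumed 2 to 4 such patients.

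A reader might go further and infer that the type I error is inflated. If dropped non-responders were replaced until 12 and 37 re-evaluated patients were reached, and if 5% is the null rate among all treated patients, a 10% dropped share would raise the null rate among those counted to 0.05/0.90 = 5.6% and the type I error to 12.4%. The documents do not support this as a finding. It needs the narrower set to govern, replacement to occur and the null to refer to all treated patients. Section 13.2's 10% over-accrual leaves room for replacement. Section 13.3, however, mentions it only as a way to supply Part 2 and keeps intolerant or off-study patients in the Part 1 rule.

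Nor can it be inferred that everyone who leaves before week 8 is lost from the denominator, given the final-visit assessment that the calendar implies.

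**What to change.** - For the primary estimate and the Part 1 decision rule, use all eligible patients who received at least one dose of trametinib. Count anyone not assessable as a non-responder. Sections 13.3 and 13.5.2 already point to this.
- Define response by the RECIST 1.1 and confirmation criteria already in Section 11.1.4, within 6 months of starting trametinib. No new response rule is needed.
- Delete the restrictive sentence in the second paragraph of Section 13.1.1, or keep that set as a labelled sensitivity analysis.
- Give evaluable the same meaning in Sections 11.1.1, 13.2 and 13.3.
- Reconcile the 45 evaluable patients in Section 13.2's decision analysis with the maximum of 37 in the same section and the 37 in Section 13.3.

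The cost is wording, with no new data and no increase in sample size. The reported response rate may be slightly lower. If the 20% target was meant only for re-evaluated patients, the stated power should be restated. With an assumed 10% not assessable, the all-treated target becomes 0.20 × 0.90 = 18%, and power falls from 90.2% to 85.7%. Section 13.2 already reports consenting in the past tense, so if the 12-patient look has taken place, the report should state which set was used for it.
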